Population:	 Maintenance Treatment Naïve COPD patients using Stiolto vs. Trelegy. Exclusion Criteria: To increase the likelihood of a true diagnosis of COPD, we will exclude all patients with two medical claims of asthma, cystic fibrosis, lung cancer, or interstitial lung disease in any position on separate dates of service during the study period. To restrict the cohort to first line maintenance therapy of Stiolto Respimat or first line maintenance therapy of Trelegy Ellipta we will exclude; patients on LAMA. monotherapy; LABA monotherapy; ICS monotherapy; free or FDC of ICS+LABA, LAMA+LABA, ICS+LABA+LAMA therapy within six months prior to index date. Pharmacy claims for multiple index medications on the index date. 		
Variables:	Moderate and Severe COPD exacerbation, Pneumonia (time to and counts), HCRU for COPD and Pneumonia; both related and attributable costs.		

Name of company:			
Boehringer Ingelheim			
Name of finished medicinal product: Stiolto/Spiolto			
Name of active ingred Tiotropium bromide	dient: + Olodaterol		
Protocol date:	Study number:	Version/Revision:	Version/Revision date:
25 October 2021	1237.0121	1.0	N/A
Title of study:	Comparison of Exacerbation Risk and Health Outcomes in Maintenance Treatment Naïve COPD patients using Stiolto vs. Trelegy.		
Data sources:	We will utilize medical and pharmacy claim records for COPD patients included in the database (previously named This database contains administrative insurance data and enrolment information derived from approximately 150 million commercially insured and Medicare lives. This longitudinal database allows documentation and analysis of the patient journey from diagnosis to intervention and follow-up. It is nationally representative covering 90% of US hospitals and compliant with current HIPAA (Health Insurance Portability and Accountability Act) regulations.		
Study size:	\sim 3000 patients in each cohort are sufficient for \geq 80% power of		
Data analysis:	Summary measures will include standard descriptive statistics (e.g., mean, standard deviation, median and range for continuous variables; counts and percentages for categorical variables).		
Milestones:	Data collection will begin in Nov 2021, interim results will be available in Dec 2021, data collection will end in Dec 2021, and the final report will be completed and be made available in Jan 2022.		

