Patients will be followed the index date to record time to first incidence of exacerbations, record time to first incident case of pneumonia, and HCRU. The analysis will be, "on treatment", analysis. Patients will be followed from the index date until the earliest of the first occurrence of outcome event, switch in index treatment (Stiolto or Trelegy), discontinuation of index treatment (Stiolto or Trelegy), the end of the study period, the end of continuous health plan eligibility, or (for main analyses) one year after index date. Hazard ratios and their 95% CI from proportional hazards models will be used to assess differences in the risk of COPD exacerbation and pneumonia.

Proprietary confidential information © 2022 Boehringer Ingelheim International GmbH or one or more of its affiliated companies

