9.2.2 Study Population

Patients initiating Stiolto, or Trelegy will be identified using pharmacy claims (database). The date of the first prescription claim (on or after 15th September 2017) will be defined as the index date. Patients will be required to have a diagnosis of COPD (ICD-9-CM: 491.xx, 492.xx, 496.xx; ICD-10-CM: J41-J44) on two separate medical claims. Patients 40 years or older will be included in the study. Patients will be required to have continuous enrolment for 12 months prior to the index date. Patients will be excluded if they show any use of COPD maintenance medications (ICS, LABA or LAMA in any combination), during the baseline period of six months pre-index date. This will satisfy the criteria for being considered as treatment naive. Patients with two separate medical claims with a diagnosis of asthma, lung cancer, interstitial lung disease, or cystic fibrosis during the study period will be excluded. Using propensity score matching (PSM) technique, we will develop matched cohorts of patients between Stiolto initiators and Trelegy initiators. We will conduct 1:1 matching using nearest neighbour matching approach with a caliper of 0.2. Exacerbation will be defined as a COPD hospitalization (severe exacerbation) or Emergency Department (ED) visit (severe exacerbation) with COPD, or use of approved respiratory antibiotics (e.g., Azithromycin) \pm Oral CorticoSteroids (OCS) medications within ± 7 days of the

Proprietary confidential information © 2022 Boehringer Ingelheim International GmbH or one or more of its affiliated companies

office/outpatient visit (moderate exacerbation) as the primary diagnosis. Multiple exacerbations occurring within 14 days of each other will be considered as a single exacerbation and will be per the higher severity.

Patients will be followed after the index date to record time to first incidence of exacerbations, record time to first incident case of pneumonia, and HCRU. The analysis will be, "on treatment", analysis. Patients will be followed from the index date until the earliest of the first occurrence of outcome event, switch in index treatment (Stiolto or Trelegy), discontinuation of index treatment (Stiolto or Trelegy), the end of the study period, the end of continuous health plan eligibility, or (for main analyses) one year after index date. Hazard ratios and their 95% CI from proportional hazards models will be used to assess differences in the risk of COPD exacerbation and pneumonia.

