9.3 VARIABLES

The definitions for exacerbations are as below.

- A severe exacerbation will be defined as follows:
 - An inpatient admission or an ER visit with a COPD diagnosis code in the primary position; or
 - An inpatient admission or an ER visit with a diagnosis code for acute respiratory failure in the primary position and a COPD diagnosis code in any position; or
 - An inpatient admission or an ER visit with a diagnosis code for acute respiratory failure in the primary position + an inpatient admission or an ER visit within ±7 days with a COPD diagnosis code in any position.
- A moderate exacerbation will be defined as follows:
 - An ambulatory (office or outpatient) visits with a COPD diagnosis code in any position + a pharmacy claim for an oral corticosteroid (OCS) prescription within ±7 days of the office/outpatient visit; or

Proprietary confidential information © 2022 Boehringer Ingelheim International GmbH or one or more of its affiliated companies

- \circ An office or outpatient visit with a COPD diagnosis code in any position + a pharmacy claim for respiratory antibiotic prescription within ±7 days of the office/outpatient visit; or
- An office or outpatient visit with a COPD diagnosis code in any position + a pharmacy claim for an OCS + a pharmacy claim for respiratory antibiotic prescription within ±7 days of the office/outpatient visit.
- Pneumonia diagnosis: Binary indicators will be created to identify patients with a diagnosis of 1) pneumonia (Appendix 1). The time to first pneumonia diagnosis, and time to first pneumonia, during follow-up will also be captured.
- Pneumonia-related hospitalization: Binary indicators will be created to identify
 patients with an acute hospitalization with diagnosis of 1) pneumonia in any
 position (Appendix 1) The time to first pneumonia-related hospitalization during
 follow-up will also be captured.
- COPD exacerbation and/or pneumonia diagnosis: Binary indicators will be created to identify patients with each of the following composite outcomes: severe COPD exacerbation or an acute hospitalization with a diagnosis of pneumonia in any position, severe COPD exacerbation or a hospitalization with a diagnosis of pneumonia in any position, any COPD exacerbation or pneumonia diagnosis in any position, and any COPD exacerbation or pneumonia diagnosis in any position. Time to event variables will be created for each composite outcome during the follow-up period.

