9.3.1 Exposures

Patients will be assigned to one of the following mutually exclusive study cohorts based on the index pharmacy claim: Stiolto Respimat or Trelegy Ellipta. Exposure measures will be based on pharmacy dispensing of the two medications under study, namely Stiolto Respimat or Trelegy Ellipta, over a follow-up period, beginning the index date and lasting up to one year from index date. Discontinuation for index medication will be defined as a gap in index medication of \geq 45 days (sensitivity analysis with \geq 30 days can be included) following the runout of days' supply (discontinuation date = runout prior to the gap in therapy). Switch in index medication will be defined as a pharmacy fill for \geq 30 consecutive days of a non-index maintenance medication (switch date = first date of the new treatment regimen). Switch includes any other change in use of index medication by active ingredient, inclusive of a change to a different combination therapy (ICS/LABA FDC, different LAMA/LABA or LAMA/LABA/ICS FDC) change from a FDC to a free form combination therapy with mono LAMA plus mono LABA, or mono ICS plus mono LABA, or mono LAMA plus mono LABA plus mono ICS or a change to a monotherapy.

Individuals in the study cohort will be followed from the index date until the earliest of the date of a switch in treatment, addition of an ICS for the Stiolto Respimat group, discontinuation of the index COPD maintenance treatment, the end of the study period, or the end of continuous health plan eligibility. Main analyses will be further limited to the first 12 months after index date, with sensitivity analyses considering all available data.

All patients will be required to be continuously enrolled in the health plan for a minimum of 12 months. The 12 months prior to and including the index date (index date – 364 through index date) will be used to assess baseline characteristics. The period starting the day after the index date, up to a maximum of 12 months duration (index date +1 through index date +365) will be used to assess exacerbation, pneumonia, HCRU and cost outcomes. Patients will be censored at the earliest of the following: discontinuation of the index medication (Stiolto or Trelegy), switch to a non-index medication, disenrollment from the health plan, 12-months following the index date, or the end of the study period.

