9.3.2.2 Secondary Outcome(s)

The secondary outcome is time to first hospitalization for community-acquired pneumonia (serious pneumonia). Pneumonia was defined using ICD-9-CM diagnoses 481.x-486.x; 487.0, 507.x, 507.0, 507.1, 507.8, 510.0, 510.9, 511.0, 513.0, 514.x, 517.1, 519.8, 530.84, and ICD-10 diagnosis codes J10.0; J11.0; J12-J18; J22; J69; J85.0; J85.1; J86. This definition has been previously used in COPD. ^{27,28}

- COPD and/or pneumonia related HCRU (including acute inpatient stays and their length of stay, emergency department visits, ambulatory [Physician office visits, hospital outpatient visits], and other medical visits)
- COPD-related HCRU
- Pneumonia-related HCRU
- COPD-attributable HCRU
- All-cause HCRU

HCRU is defined as total inpatient, emergency department, and outpatient care episodes. Estimates will be presented both overall and for COPD and/or pneumonia-related care, defined as claims where a diagnosis of COPD or pneumonia is present. Medications used, defined as total number of distinct medication subclasses dispensed (e.g., 4-digit level of the Generic Product Identifier) and total number of dispensing for medications per year. COPDrelated medication utilization included all COPD medications, OCS, and guidelinerecommended antibiotics

Annual HCRU costs (including costs paid by the patient, health plan, and any third party via coordination of benefits) will be then calculated as total costs, medical costs, pharmacy costs, ambulatory costs, ED costs, inpatient costs, and other costs. Costs were defined as related to COPD if the claim has a diagnosis for COPD in any position or is a pharmacy claim for a medication used to treat COPD. The sum of all costs from all care settings and pharmacy dispensing will be assessed overall, for COPD and/or pneumonia-related care.

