APPENDIX 3: COPD GUIDELINE-RECOMMEND ANTIBIOTIC MEDICATIONS

Drug Category	Drug Class	Medication	
COPD Guideline-		cefaclor	
recommended Antibiotics ¹		cefdinir	
		cefditoren	
		cefepime	
	Cephalosporins	cefpodoxime	
		cefprozil	
		ceftibuten	
		ceftriaxone	
		cefuroxime	
	M	azithromycin	
	Wacrondes	clarithromycin	
		amoxicillin	
	Penicillins	amoxicillin/potassium	
		piperacillin/tazobactam	
		levofloxacin	
	Quinoiones	moxifloxacin	
	Sulfonamide	sulfamethoxazole/trimethoprim	
	combinations		
	Tetracyclines	doxycycline	

¹The American Thoracic Society (2017) and Global Initiative for Chronic Obstructive Lung Disease (2020) guidelines recommend that antibiotics for acute exacerbation of chronic bronchitis be selected based on local sensitivity patterns. For more specific recommendations, The Sanford Guide to Antimicrobial Therapy (2020) was referenced.

COPD Exacerbation Definition

- **Exacerbation Hierarchy:** Exacerbation events will be classified as severe or moderate according to the highest severity contributing event.
- **Exacerbation Episodes:** Exacerbations occurring within 14 days of each other will be considered a single exacerbation episode and will be classified according to the highest severity contributing event.
- Episode Length: The start date of the exacerbation episode will be the service date of the first event (medical encounter or pharmacy fill for an OCS or antibiotic). The end date of the exacerbation episode will be defined as the last observed exacerbation event date (or discharge date if an inpatient event) + 14 days.

Proprietary confidential information © 2022 Boehringer Ingelheim International GmbH or one or more of its affiliated companies

• Single Event Episode

- In a single event episode, the exacerbation begins with the earliest occurrence of these events: COPD exacerbation defined inpatient admission, ER visit, ambulatory visit, or corticosteroid or antibiotic dispensing as defined in Section 9.3.2.1. In a single event episode, the exacerbation ends 14 days from the start of the event, hospital discharge, or following the OCS or antibiotic dispensing, whichever is later.
- *Episode Start date* = service date of a qualifying event (inpatient admission, ED visit, ambulatory visit, or OCS or antibiotic dispensing).
 - If the qualifying event is a hospitalization, the start date is the admission date.
 - If the qualifying event is an ED visit, the start date is the service date.

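### Pneumonia is called an incident outcome but no pneumonia-free interval is required, so a claim after index for a pneumonia that began before it is scored as a first on-treatment event

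*Combined protocol and SAP*

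**What the plan says.** Sections 9.1 and 9.2.2 state the intention in the same terms: follow-up is to "record time to first incident case of pneumonia".

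The operational definitions are in three places:

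- Section 9.3, any diagnosis: "The time to first pneumonia diagnosis, and time to first pneumonia, during follow-up will also be captured". Section 9.3 also defines a composite of any COPD exacerbation or any pneumonia diagnosis.
- Section 9.3, hospitalization: an indicator for "patients with an acute hospitalization with diagnosis of 1) pneumonia in any" position, with time to the first such stay.
- Section 9.3.2.2, the formal outcome: "The secondary outcome is time to first hospitalization for community-acquired pneumonia (serious pneumonia". A code list follows, with no condition on earlier pneumonia.

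Section 9.3.1 sets the outcome window: "The period starting the day after the index date, up to a maximum of 12 months duration". Section 9.3 assigns claims dated on the index date to baseline, apart from the index medication. Section 9.3.3 lists a baseline pneumonia diagnosis among the propensity score covariates, with no recency window.

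Exacerbations are treated differently. The exacerbation definition at the end of Appendix 3 has a grouping rule ("Exacerbations occurring within 14 days of each other will be considered a single exacerbation episode") with start, end and extension logic. Section 9.3.3 also measures prior exacerbation in the 30 days before cohort entry as well as overall. Pneumonia has neither.

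The abstract lists pneumonia among the variables as "Pneumonia (time to and counts"), but no section says what one countable pneumonia is.

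**The concern.** A pneumonia that began before the first fill cannot have been caused by the index drug. Under the written definitions, however, any further claim for it dated index + 1 or later becomes the patient's first pneumonia on that drug and ends follow-up for that outcome.

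If this happens equally often in both cohorts, it adds events unrelated to treatment and pulls the hazard ratio toward 1. If one product is started more often during or just after pneumonia, it biases the ratio toward or away from 1, depending on which product. The second case is plausible here: the background section links triple therapy to recent exacerbations, and sections 9.2.4 and 9.7 anticipate channeling.

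The background presents the choice between the two regimens as a trade-off between preventing exacerbations and raising pneumonia risk. Pneumonia is therefore the main harm comparison, and its definition should match its label.

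**Working it through.** **Does any rule remove carried-over pneumonia?** The plan gives no figure to reproduce on this point, so the first step is to set the rules side by side.

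| Rule | Exacerbation | Pneumonia |
|---|---|---|
| Repeat claims grouped into episodes | Yes, 14-day gap (Appendix 3) | None |
| Date assigned to a hospital stay | Admission date (Appendix 3) | Not stated |
| Covariate for the 30 days before index | Yes (9.3.3) | None; baseline diagnosis only |
| Clean interval, lag or exclusion | None | None |
| Index-date claims sent to baseline | Yes (9.3) | Yes (9.3) |

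Take a patient with pneumonia coded 3 days before index and a follow-up visit coded for it at index + 5. The visit lies inside the outcome window and is the first pneumonia diagnosis there, so it counts. The index-date rule does not reach it. The propensity covariate makes this patient comparable to others with any baseline pneumonia, including pneumonia from months earlier.

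**Which outcomes are exposed?**

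- Any pneumonia diagnosis, and any exacerbation or pneumonia diagnosis: fully, because any coded follow-up visit qualifies.
- Pneumonia hospitalization (9.3.2.2): only a readmission for the same pneumonia, or a stay that spans index if it is not dated by admission. Outpatient visits cannot qualify.

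**Illustration for the any-diagnosis outcome.** Inputs:

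- *r*, new-event risk: 14.5% (Stiolto) and 19.3% (Trelegy), the pneumonia proportions quoted in section 9.5 from an earlier claims study. Treating them as free of carry-over is an assumption.
- *c*, share of patients whose pre-index pneumonia is scored as a first event: assumed, since the documents give no value.
- 3018 matched patients per group (section 9.5).

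Observed risk is *p* = *c* + (1 − *c*)*r*, and the hazard ratio (Trelegy/Stiolto) is approximated as ln(1 − *p*T)/ln(1 − *p*S). Section 9.7.1 reports Stiolto relative to Trelegy, the reciprocal.

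Without carry-over: ln(0.807)/ln(0.855) = 0.2144/0.1567 = 1.37.

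| Carry-over Stiolto / Trelegy | Observed risk Stiolto / Trelegy | Hazard ratio |
|---|---|---|
| 1% / 1% | 15.4% / 20.1% | 1.35 |
| 2% / 2% | 16.2% / 20.9% | 1.33 |
| 5% / 5% | 18.8% / 23.3% | 1.28 |
| 2% / 4% | 16.2% / 22.5% | 1.44 |
| 4% / 2% | 17.9% / 20.9% | 1.19 |

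Each 1% of carry-over is 0.01 × 3018, or about 30 patients per arm whose recorded first event is a carried-over claim.

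**If there is no true difference** (14.5% in both arms), carry-over of 2%/4% gives observed risks of 16.2% and 17.9% and a hazard ratio of about 1.12. The difference is 0.0171 with standard error √[(0.1621 × 0.8379 + 0.1792 × 0.8208)/3018] = 0.0097, so *z* is about 1.77. The chance of a significant result in that direction at two-sided 0.05 (assumed from the planned 95% intervals) is Φ(1.77 − 1.96), about 42%. Carry-over of 1%/2% gives a hazard ratio of about 1.06 and a chance of about 15%.

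**The case against.** The strongest reply concerns scope. The formal secondary outcome is hospitalization, not diagnosis, and post-discharge visits or repeat imaging cannot score there. If pneumonia stays were dated by admission, as Appendix 3 does for exacerbations, stays spanning index would drop out as well and only readmissions would remain. This stands: a reader might infer that the formal pneumonia comparison is exposed to the full effect, and the documents do not support that. The admission-date convention is not, however, stated for pneumonia.

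Second, the plan has relevant safeguards. Index-date claims go to baseline. The propensity score includes baseline pneumonia, exacerbation in the prior 30 days, acute bronchitis, respiratory antibiotics, oral corticosteroids and dyspnea, plus data-derived variables (9.7.1). Imbalance above 10% triggers adjustment or possible discontinuation. These make differential carry-over less likely but do not remove it: they do not directly balance pneumonia active at index, and balance alone would still leave attenuation.

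Third, two stronger readings should be set aside. A reader might infer that every later claim for one pneumonia inflates a count. Section 9.3 specifies binary indicators and time to first event, which repeat claims do not inflate; counts appear only in the abstract, and the text supports no more than that the counting unit is undefined. A reader might also want to dilute the hazard ratio of 1.46 quoted in section 9.5. That figure is for severe pneumonia requiring hospitalization, whereas the 14.5% and 19.3% come from a different study of pneumonia diagnoses. Combining them describes no outcome in this plan.

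Finally, the carry-over share has no anchor in the documents. That also stands, and the table above shows sensitivity to an assumption, not an expected bias.

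**Conclusion.** The concern holds in limited form. The label promises incident pneumonia; the definitions deliver the first pneumonia code after index, whenever the illness began. Followed as written, the plan scores carried-over claims as first on-treatment events. This is a defect of definition and does not depend on any assumed number.

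Its size does. For the any-diagnosis outcome, a hazard ratio of about 1.37 moves to between 1.28 and 1.35 under equal carry-over of 5% to 1%, and to 1.44 or 1.19 when carry-over is twice as common in one arm (2% against 4%). These results take the cited proportions as new-event risks, approximate the hazard ratio from one-period risks, and ignore on-treatment censoring. No size can be given for pneumonia hospitalization, where the exposure is smaller. The definition should be corrected before the comparative analysis; nothing here shows that the pneumonia comparison is invalid.

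**What to change.** In sections 9.3 and 9.3.2.2:

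1. Define the start of a pneumonia episode as a pneumonia claim with no pneumonia claim in a stated preceding interval, with the look-back running across the index date. For example, use 30 days, with 14 days, the plan's own exacerbation gap, as a sensitivity value.
2. Count a diagnosis or hospitalization as an outcome only if its episode began after index. Tie the condition to the episode: otherwise an outpatient claim a few days before admission would disqualify a genuinely new hospitalized pneumonia.
3. Date hospitalizations by admission, so that stays spanning index are not outcomes.
4. If pneumonia counts are reported, use the same gap as the counting unit.

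In section 9.3.3, add pneumonia in the 30 days before index to the propensity score and the balance table. In section 9.7.1, repeat the pneumonia analyses excluding those patients, stating whether their matched pairs are dropped or the match is rerun.

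The cost is a few lines of code on claims already held, plus a refit of the propensity score, which may move the matched total slightly from 3018 per group. The downside is that a few genuine early recurrences will not be counted.

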8. RESEARCH QUESTION AND OBJECTIVES

The goal of this study is to investigate the risk of COPD exacerbations, community acquired pneumonia, and health care utilization in maintenance treatment naïve patients treated as first line therapy with Fixed Dose Combination (FDC) of Tiotropium + Olodaterol (Stiolto, 5/5 mcg), in comparison to maintenance treatment naïve patients treated with first line therapy, FDC of Fluticasone Furoate + Umeclidinium + Vilanterol (Trelegy, 100/62.5/25 mcg). Primary and Secondary analyses will be conducted for the total population and

Primary objective:

- To characterize the COPD patient population who are maintenance treatment naïve and initiated Trelegy or Stiolto as the first line therapy.
- To compare the effectiveness of Stiolto (new treatment initiation) with Trelegy (new treatment initiation) for time to the first COPD exacerbation (moderate/severe) in COPD patients who are maintenance treatment naïve.
- To compare COPD exacerbations following initiation of Stiolto (new treatment initiation) with initiation of Trelegy (new treatment initiation)

Secondary objectives:

- To compare the effectiveness of Stiolto (new treatment initiation) with Trelegy (new treatment initiation) for time to the first hospitalization of community acquired pneumonia in COPD patients who are maintenance treatment naïve.
- To assess differences between Stiolto vs Trelegy in, "all-cause" and "COPD and/or pneumonia-related", HCRU and HCRU cost (total population and sub-groups by care setting).

9. **RESEARCH METHODS**

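### The secondary outcome is named hospitalization for community-acquired pneumonia, but no stated rule makes a counted stay community-acquired or due to pneumonia, and the resulting bias can go in either direction

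*Combined protocol and SAP*

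**What the plan says.** Section 8 sets the secondary objective as a comparison "for time to the first hospitalization of community acquired pneumonia in COPD patients who are maintenance treatment" naïve. Section 9.3.2.2 repeats it: "The secondary outcome is time to first hospitalization for community-acquired pneumonia". That section then lists codes. The ICD-10 part is "ICD-10 diagnosis codes J10.0; J11.0; J12-J18; J22; J69; J85.0; J85.1; J86", and the ICD-9 part includes "507.x, 507.0, 507.1, 507.8, 510.0, 510.9, 511.0, 513.0, 514.x, 517.1, 519.8, 530.84". The list is supported by one sentence, "This definition has been previously used in COPD", with two references. The section gives no diagnosis position, no onset rule and no washout.

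Section 9.3 separately defines a variable called pneumonia-related hospitalization, which identifies "patients with an acute hospitalization with diagnosis of 1) pneumonia in any" position. It takes its codes from Appendix 1. As shown, Appendix 1 contains only codes for acute respiratory failure and related conditions.

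The first branch of the severe-exacerbation rule in Section 9.3 reads: "An inpatient admission or an ER visit with a COPD diagnosis code in the primary position". It does not exclude stays with a secondary pneumonia code.

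**The concern.** The outcome as named makes two claims about each counted stay: pneumonia was the reason for admission, and it was acquired outside hospital. Neither claim is built into any rule. A present-on-admission, principal-diagnosis or prior-discharge condition would do it, and the protocol has none for this outcome.

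This matters because the rationale in Section 7 rests on the pneumonia risk of adding an inhaled corticosteroid, weighed against preventing exacerbations. If the pneumonia outcome contains other kinds of admission, its hazard ratio mixes the effect of interest with the treatment contrast in those admissions. If one stay can count on both sides of the trade-off, the two results are harder to read against each other.

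**Working it through.** **Step 1. Set the sections side by side.**

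| Element | Section 8 and 9.3.2.2 | Section 9.3 |
|---|---|---|
| Name | hospitalization for community-acquired pneumonia | pneumonia-related hospitalization |
| Codes | listed, including J22, J69, 507.x | Appendix 1 (respiratory failure only, as shown) |
| Position | not stated | any |
| Onset or clean period | none | none |

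The protocol draws the missing distinction elsewhere. For resource use and costs, Section 9.3 calls any-position claims 'related'. It calls claims 'attributable' when the code is primary, or when respiratory failure is primary and COPD or pneumonia is secondary.

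**Step 2. What the only stated position rule lets in.**
- Stays for another reason with a secondary pneumonia code.
- Hospital-onset events, and aspiration events if the 9.3.2.2 list applies. Reading J69 as aspiration and J22 as unspecified lower respiratory infection comes from the ICD classification, not the protocol. The point does not depend on it.
- COPD-primary stays with secondary pneumonia, which also meet the severe-exacerbation rule.
- Continuations of a pre-index pneumonia. Outcomes are assessed from the day after index (Section 9.3.1), and baseline pneumonia is a matching covariate (Section 9.3.3), not an exclusion.

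**Step 3. Direction and size.** The plan gives no figure for this outcome. Its statement of at least 80% power (Section 9.5) carries no effect, alpha or event rate, so it cannot be reproduced.

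Hazard ratios here are triple relative to dual therapy; the plan's own HR (Section 9.7.1) is the reciprocal. Inputs from Section 9.5:
- True HR 1.46 for severe pneumonia requiring hospitalization.
- Severe exacerbation 9.0% on tiotropium/olodaterol versus 16.1% on triple therapy, a ratio of 16.1/9.0 = 1.79, used as a stand-in for a hazard ratio.
- Exacerbation HR 0.83 in patients with two or more prior exacerbations.

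Assumption: a share f of counted Stiolto-arm stays does not qualify, and those stays have hazard ratio h0. Then

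observed HR = (1 − f) × 1.46 + f × h0.

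At f = 30%: 0.7 × 1.46 + 0.3 × 1.00 = 1.32, and 0.7 × 1.46 + 0.3 × 1.79 = 1.56.

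| f | h0 = 0.83 | h0 = 1.00 | h0 = 1.46 | h0 = 1.79 |
|---|---|---|---|---|
| 20% | 1.33 | 1.37 | 1.46 | 1.53 |
| 30% | 1.27 | 1.32 | 1.46 | 1.56 |
| 50% | 1.15 | 1.23 | 1.46 | 1.62 |

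If the share is instead taken over both arms pooled, the h0 = 1 column becomes about 1.35, 1.30 and 1.21.

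**Step 4. Cost of a stricter rule.** Assume a true risk of 3% in the Stiolto arm, 3018 patients per arm (Section 9.5), two-sided alpha 0.05, and a stricter rule with no false positives. Expected events are 3018 × 0.03 × (1 + 1.46) × sensitivity.

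| Sensitivity | Events | Power for HR 1.46 |
|---|---|---|
| 100% | 223 | 0.81 |
| 80% | 178 | 0.71 |
| 60% | 134 | 0.59 |

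At an assumed 2% risk the three powers are 0.64, 0.54 and 0.43; at 4% they are 0.90, 0.83 and 0.71. For comparison, the broad rule at 3% true risk, with f = 30% and h0 = 1, has about 300 events and power 0.68.

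**The case against.** Four arguments favour leaving the plan alone.

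- *No section states the broad rule as the secondary endpoint.* The any-position wording belongs to one variable and the code list to another. This is correct, and it limits the finding: the two sections leave the definition open. A reader might infer that any-position coding with J22 and J69 is the declared endpoint, but that reading joins two sections that the protocol does not join.
- *The code list has precedent in COPD.* This stands for the list. The sentence says nothing about position, onset or accuracy.
- *Misclassification and bias analysis are acknowledged in Section 9.9, and baseline pneumonia is matched on.* The acknowledgement is general, and no pneumonia sensitivity analysis is specified. Matching limits imbalance between arms in carried-over codes but does not remove those events.
- *A primary-position rule discards true events.* Some COPD-primary stays include genuine community-acquired pneumonia, and some aspiration begins in the community. This stands, and Step 4 shows the cost. It argues for reporting both versions rather than simply replacing one with the other.

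**Conclusion.** The concern holds as a gap in definition. The outcome is named as community-acquired pneumonia hospitalization, the sections that should define it do not agree, and the only position rule stated does not restrict events to that condition.

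A reader might go further and infer that the extra stays dilute the corticosteroid pneumonia signal. The documents do not support a fixed direction. Dilution requires the extra stays to be unrelated to treatment or less affected by it than true pneumonia is. The cited study of tiotropium/olodaterol against triple therapy shows more severe exacerbations on triple therapy, which would push the estimate up. At a 30% share the observed HR could be about 1.32 or about 1.56 for a true 1.46.

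These figures rest on an assumed share and on 1.46 being the effect on a fully specific outcome. The cited cohort's coding rule is not in the documents, so misclassification may already be present in 1.46. It would also be too strong to say that the study cannot address its secondary objective; with a reconciled definition and a specific version, it can.

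**What to change.** 1. State one definition, with codes, diagnosis position and clean period, in both 9.3 and 9.3.2.2, and make the Appendix 1 reference point to the pneumonia codes.
2. Require no pneumonia-coded inpatient stay in a stated window before the event. Thirty days is an example; the documents give no basis for a particular length.
3. Prespecify a specific version: J10.0, J11.0 or J12-J18 in primary position, or acute respiratory failure primary with one of these secondary. This adapts the protocol's own 'attributable' rule. Report it beside the broad version (any position, full list).
4. Report how many counted stays also qualify as severe exacerbations.
5. If the broad version stays as the main analysis, call it pneumonia-related hospitalization.

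The work is protocol wording and re-use of fields already needed for the resource-use analysis. The price is precision. The specific version has fewer events, loses some true pneumonia coded second to COPD, and has a wider confidence interval, as Step 4 shows. Keeping the broad version beside it preserves comparability with earlier work.
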